TITLE:

Dose Intensification with a Focal Boost to Dominant Intraprostatic Lesion using Volumetric Modulated ArcTherapy /Image Guided Radiotherapy in Patients with Localized Prostate Cancer

ClinicalTrials.gov Identifier: NCT03030625 **Version**: 8, 18th November 2020

ABSTRACT:

Prostate cancer is a multi-focal disease and conventional therapies address this by treating the whole gland. However, numerous evidence coming from prostate pathology studies suggest the existence of a dominant cancer focus or dominant lesion (DL) within the gland that may be the nucleus of the aggressiveness of the cancer and therefore of recurrence post treatment. Thus strategies to identify and intensify treatment to this DL are under active investigation. Advances in multiparametric magnetic resonance imaging (mpMRI) have shown promising results in identifying focal lesions and advances in high accuracy radiotherapy have enabled dose intensification.

Hypothesis

The hypothesis is that differential boosting with focal dose escalation delivered by VMAT to an imaging (mpMPR) defined DL within the prostate is associated with a higher PSA, clinical (mpMRI) and histological control without a significant increase in toxicity (both acute and late) in males with localized prostate.

Objectives

The aim of this study was to determine the efficacy and safety of the implementation of a program of " image-guided focal Intensification dose to intraprostatic dominant lesion " in men with localized prostate cancer (PCa) of intermediate and high risk (criteria NCCN) eligible to receive radiotherapy in the Department of Radiation Oncology of HUP within the established dose escalation protocol with intensity modulated image-guided radiotherapy (IMRT / IGRT).

Primary objectives:

- To increase biochemical and local control of patients localized PCa of intermediate and high- risk.

- To maintain or decrease the incidence of acute and late urinary rectal complications despite increased dose (focal) radiotherapy.

Secondary objectives:

- Biochemical disease-free survival at 3 yrs (according to RTOG-ASTRO Phoenix Consensus Conference criteria).

- Assessment of the quality of life perceived by the patient in the urinary, digestive and hormone domains.

- To determine the impact of treatment on the disease-free survival (DFS).

- To assess the adequacy of the safety margins of the treatment volume and the possibility of reducing these margins to minimize the risk of complications when incorporating specific immobilization.

SAMPLE SIZE 37 PATIENTS

STUDY VARIABLES DEFINITION

- 1. Patients were counted as biochemical failures according to the Phoenix definition (PSA >2 ng/mL above the currently observed PSA nadir). The Kaplan- Meier method was used to estimate the probability of biochemical control and of DFS.
- 2. Biochemical relapse-free survival (bRFS) was calculated from the time of first radiation treatment to failure, last follow-up or death. PSA nadir was set to be the lowest PSA value following treatment completion. Benign bounce was defined as nadir +0.2 ng/ml as long as subsequent PSAs after the bounce dropped lower than the relative nadir before the bounce.
- 3. Morphological and functional response was evaluated by mpMRI at 12 months after radiotherapy and compared to the baseline scans.
- 4. Acute toxicity was assessed in terms of the incidence and severity of genitourinary (GU) and gastrointestinal (GI) adverse events from 48 h until 3 months after the procedure.
- 5. Late toxicity defined as the maximal toxicity per patient more than 90 days after completion of RT Late adverse effects of radiation assessed at each follow-up visit using the radiation morbidity scoring criteria of the European Organization for Research and Treatment of Cancer Radiation Therapy Oncology Group (EORTC/RTOG) and The Common Terminology Criteria for specific Adverse Events.

The incidence of late adverse effects was calculated as the occurrence of the maximum grade toxicity per patient divided by the number of patients in each arm. The c2 or Fisher exact test was used to evaluate differences in patient and treatment characteristics for categorical variables. The t test, analysis of variance, or Mann-Whitney test was used, depending on the type and distribution of the variables, to evaluate differences in patient and treatment characteristics for continuous data. The cumulative incidence method was used to estimate time to late toxicity, and treatment groups were compared using the log-rank test. Death from any cause was considered a competing risk.

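### The plan sets no limit for an acceptable toxicity rate, so its wording invites a safety conclusion from a non-significant difference in 37 patients

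*Combined protocol and SAP*

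**What the plan says.** Safety is framed in two places in the combined protocol and SAP. Under Hypothesis, the focal boost is expected to improve control "without a significant increase in toxicity (both acute and late) in males with localized prostate". Under Primary objectives, the second aim is "To maintain or decrease the incidence of acute and late urinary rectal complications despite increased dose (focal) radiotherapy".

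The methods are under STUDY VARIABLES DEFINITION:

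- Acute toxicity (item 4) is described by the incidence and severity of "adverse events from 48 h until 3 months after the procedure". No test or threshold is attached.
- Late toxicity (item 5 and the closing paragraph) is the maximum grade per patient, "divided by the number of patients in each arm". Time to late toxicity is estimated by cumulative incidence with death as a competing risk, and "treatment groups were compared using the log-rank test".
- The remaining tests concern baseline and treatment variables: the chi-square or "Fisher exact test was used to evaluate differences in patient and treatment characteristics for categorical variables".

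The size is given as "SAMPLE SIZE 37 PATIENTS", without a calculation. The documents state no reference toxicity rate, qualifying grade, maximum acceptable rate or difference, significance level or confidence-limit criterion. Arms and treatment groups are mentioned but not defined.

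**The concern.** A primary objective of keeping toxicity level needs a statement of what result would support it. Here the only inferential tool for toxicity is a test of difference, and the hypothesis is worded as the absence of a significant increase. Failing to reject equality does not show that rates are equal, and the fewer the patients, the easier it is to fail to reject. Naming a comparator would not cure this: even with a perfectly known reference rate, non-significance would not show that complications were maintained.

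The programme intensifies dose. If non-detection is read as safety, the error runs against patients, and a reader of the report could not tell which of the two had happened.

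**Working it through.** **The plan's own figure.** The 37 cannot be reproduced, because no rate, margin, significance level or power is given. It is taken as fixed.

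**Inputs.** n = 37 is from the document. All else is assumed: one arm, no dropout, reference rate p0 known without error and ranging from 5% to 30%, and an exact binomial test at one-sided 0.025 or 0.05.

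**Step 1: chance of missing a doubling.** The critical count r is the smallest r with P(X ≥ r | 37, p0) ≤ α. The miss probability is P(X ≤ r − 1 | 37, 2·p0).

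| p0 → 2·p0 | r at 0.025 (attained level) | Missed | r at 0.05 (attained level) | Missed |
|---|---|---|---|---|
| 5% → 10% | 6 (0.0095) | 84% | 5 (0.0359) | 69% |
| 10% → 20% | 9 (0.0093) | 69% | 8 (0.0274) | 53% |
| 15% → 30% | 11 (0.0169) | 42% | 10 (0.0419) | 29% |
| 20% → 40% | 13 (0.0231) | 22% | 13 (0.0231) | 22% |
| 25% → 50% | 16 (0.0117) | 16% | 15 (0.0272) | 9% |
| 30% → 60% | 18 (0.0131) | 6% | 17 (0.0295) | 3% |

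With the same critical counts, a 1.5-fold rise is missed 91% (82%) of the time from 10% to 15%, and 61% (48%) from 30% to 45%.

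**Step 2: other layouts.** If 37 is the total and is split 18 and 19, a two-sided Fisher test at 0.05 misses a doubling 98%, 93%, 87%, 80% and 59% of the time from 5%, 10%, 15%, 20% and 30%. With 37 per group the figures are 96%, 86%, 75%, 62% and 34%. Fisher's test stands in for the planned log-rank test, which cannot be evaluated without event times.

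**Step 3: what an interval would show.** The Clopper-Pearson 95% limits for x events are the 0.025 quantile of Beta(x, 38 − x) and the 0.975 quantile of Beta(x + 1, 37 − x).

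- 0/37: upper limit 1 − 0.025^(1/37) = 9.5%.
- 4/37 (10.8%): 3.0% to 25.4%.
- 8/37 (21.6%): 9.8% to 38.2%. Against a 10% reference, P(X ≥ 8) = 0.0274. More than twice the reference rate would thus be non-significant at one-sided 0.025, although the interval reaches 38.2%.

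**Step 4: can 37 patients meet a limit-based criterion?** Suppose the maximum is set, for illustration, at twice p0 and the true rate equals p0. Let c be the largest count whose exact 95% upper limit lies below 2·p0. The chance of success is P(X ≤ c | 37, p0).

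| p0 | c | Upper limit at c | Chance of success |
|---|---|---|---|
| 5% | 0 | 9.5% | 15% |
| 10% | 2 | 18.2% | 27% |
| 15% | 5 | 28.8% | 51% |
| 20% | 8 | 38.2% | 69% |
| 25% | 12 | 49.8% | 89% |
| 30% | 15 | 57.9% | 94% |

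For 80% power at one-sided 0.025, the level that matches a 95% interval, the exact sizes are 231, 107, 61, 45 and 22 patients at p0 = 5%, 10%, 15%, 20% and 30%. At one-sided 0.05 they are 179, 82, 49, 36 and 19.

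**The case against.** The strongest reply is that the documents contain no decision rule at all. The word significant appears in one clause of a hypothesis, may be meant clinically, and comes with no p-value threshold. The primary objective is worded differently, as level or lower. This stands in part: a reader might infer that the plan formally declares safety when a test is non-significant, and the documents do not say so. It does not remove the point, because a clinical reading also needs a limit, and level or lower gives a direction without a number.

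A reader might also infer that the plan offers nothing but tests of difference. It does not support that: crude incidence and cumulative incidence are both planned, most of the named tests concern patient and treatment characteristics, and acute toxicity has no test.

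A third tempting reading is that a doubled complication rate would often pass unnoticed whatever its level. The figures do not bear this out. In a single arm against a known rate, few doublings are missed once the reference is 25% to 30%, and with no grade threshold stated such rates cannot be excluded. Part of the high miss rate at 5% and 10% also reflects the conservatism of the exact test, whose attained level is below 0.01 there. In the other direction, treating the reference as known favours the plan, and the two-group layouts miss more.

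Finally, the text is in the past tense at version 8, so it may be too late to set a limit blind to the toxicity data. That is a fair limit on the remedy, and the fix allows for it.

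**Conclusion.** The point holds in a conditional form. The hypothesis and the primary objective invite a safety conclusion from a non-significant difference, and the plan states no criterion that a toxicity result would have to meet. That gap does not depend on any assumed rate.

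Its size does. Under the single-arm assumptions at one-sided 0.025, a doubling is missed in 69% to 84% of trials at reference rates of 5% to 10%, in 22% to 42% at 15% to 20%, and in 6% to 16% at 25% to 30%. Smaller rises remain hard to see even for common events. The plan should be changed, but its planned toxicity estimates remain usable.

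**What to change.** 1. Report acute and late urinary and rectal toxicity rates each with an exact 95% confidence interval, and give the planned cumulative incidence of late toxicity with its interval.
2. State that a non-significant test will not be reported as no increase.
3. Call a rate maintained only if its upper limit lies below a maximum that the sponsor justifies and sets before examining the toxicity data.
4. If no such maximum is set, or the data have already been seen, state that the trial estimates toxicity and does not conclude that it is not increased.

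This changes the wording of the hypothesis, the objective and the conclusion, with no added patients or visits. The cost is a more modest claim. If the maximum were a doubling, 37 patients would usually fail to exclude it at reference rates of 5% or 10%, would do so about half the time at 15%, and would approach conventional power only from about 20% upwards. At low rates the practical outcome is therefore the estimation statement in item 4.

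### Does the benign-bounce definition leave it open whether a PSA rise above 2 ng/mL counts as a failure in bRFS?

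*Combined protocol and SAP*

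**What the plan says.** Study Variables Definition, item 1, sets the counting rule: "Patients were counted as biochemical failures according to the Phoenix definition (PSA >2 ng/mL above the currently observed PSA nadir"). It states no exception.

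Item 2 sets the time scale: "Biochemical relapse-free survival (bRFS) was calculated from the time of first radiation treatment to failure, last follow-up or death". It then describes the nadir ("PSA nadir was set to be the lowest PSA value following treatment completion") and the bounce: "Benign bounce was defined as nadir +0.2 ng/ml", on condition that later values go under the nadir that preceded it ("as long as subsequent PSAs after the bounce dropped lower than the relative nadir before the bounce"). It gives the bounce no maximum rise, no time window and no role in the analysis.

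The Secondary objectives list "Biochemical disease-free survival at 3 yrs (according to RTOG-ASTRO Phoenix Consensus Conference criteria"). Biochemical control is also among the Primary objectives. The stated sample size is 37, with no inputs behind it.

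**The concern.** The bounce sentence stands inside the item that defines bRFS, straight after the sentences on failure and nadir. A reader may therefore suppose that it is meant to affect the endpoint. A rise of 2 ng/mL or less is never a Phoenix failure, so the bounce rule could alter bRFS only where the rise exceeds 2 ng/mL and later reverses. In that region both definitions are met, and no sentence ranks them.

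If a bounce cancelled the failure, classification at the event visit would depend on PSA values collected afterwards. Two patients with the same rise could be classed differently only because one was followed longer. With 37 patients, a single reclassification would be visible in the reported control rate.

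**Working it through.** The plan gives no figure to reproduce here. The check applies the two rules to assumed PSA series and then compares the passages.

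**Rules as coded**
- Failure: PSA minus the running nadir (lowest value so far) is above 2 ng/mL, from item 1.
- Bounce: PSA minus the running nadir is at least 0.2 ng/mL, and later values fall below that nadir, from item 2. Reading 0.2 as a minimum is an assumption, because the text has no comparison sign.

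**First assumed series.** PSA at months 3, 6, 12, 18, 24, 36: 1.5, 0.8, 0.6, 2.8, 0.5, 0.3. At month 18 the rise is 2.8 − 0.6 = 2.2.

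| Follow-up ends | Failure at month 18? | Bounce? |
|---|---|---|
| Month 18 | yes | no later value |
| Month 24 | yes | yes (0.5 < 0.6) |
| Month 36 | yes | yes (0.5 and 0.3 < 0.6) |

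With 2.5 at month 18 the rise is 1.9. There is no failure at any cut-off, so the bounce rule has nothing to act on.

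**Second assumed series.** PSA at months 3, 6, 12, 18, 24, 30, 36: 1.2, 0.8, 0.5, peak, 0.9, 0.4, 0.3. Here any later value below the earlier nadir is taken as enough for a bounce.
- Peaks 0.7, 1.5 and 2.4 (rises 0.2, 1.0, 1.9): bounce only.
- Peaks 2.6 and 3.0 (rises 2.1, 2.5): both rules met.
- Peak 3.0 with follow-up cut at month 24: failure only.

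The overlap is therefore real under the minimum-rise reading. The failure column does not change with follow-up, however. Only the bounce label does, as it must for any definition of a rise that later reverses.

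**Size, if a failure were cancelled**
- Crude rate: 1/37 = 2.7 points; two patients, 2/37 = 5.4; three, 3/37 = 8.1.
- Kaplan-Meier step with no earlier failure and 30, 25 or 20 patients at risk (assumed): 1/30 = 3.3, 1/25 = 4.0, 1/20 = 5.0 points.
- Direction: the estimate rises if the patient has no later failure, but it need not otherwise. A failure at month 18 with 30 at risk gives 29/30 = 96.7%. Cancel it, let the same patient fail at month 30 with 20 at risk, and the estimate is 19/20 = 95.0% (assumed figures, no other failures).

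**Passages side by side**
1. Item 1 defines failure by Phoenix, with no exception.
2. Item 2 uses the word failure for the bRFS endpoint without redefining it.
3. The 3-year secondary endpoint names Phoenix again.
4. The bounce sentence names a pattern. It does not say that the pattern excludes, delays or reverses a failure.

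Points 1 to 3 give one rule, and point 4 does not amend it.

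**The case for a change.** The strongest case on the other side is that no bounce outcome is listed anywhere, so a definition with no analysis attached invites the inference that it was meant to qualify failure. The nadir wording adds to this. Item 1 uses the nadir as it stands at each visit ("PSA >2 ng/mL above the currently observed PSA nadir"), while item 2 can be read as the lowest value over all follow-up. If only values after that overall lowest point are judged, the second series has no failure even with peaks of 2.6 and 3.0, because its lowest value (0.3) is the last one. A short clarification would cost almost nothing.

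Part of this stands: the purpose of the bounce label is unstated, and a sentence saying that it is descriptive would do no harm. The rest does not carry the point. A missing purpose is not an instruction to override item 1. The heading of the section is about defining variables, and a descriptive term fits there. The two nadir sentences are compatible if the nadir is the lowest post-treatment value up to the visit being judged. Item 2's own bounce wording supports this, since it speaks of a nadir before the bounce that later values go below, and such a nadir cannot be the lowest of all follow-up. Finally, if the 0.2 is read as a ceiling, a bounce can never exceed 2 ng/mL above nadir and the overlap disappears.

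**Conclusion.** The concern does not call for a change. It identifies missing detail that an analyst following the text would fill in one way: failure is the first post-treatment PSA more than 2 ng/mL above the nadir seen so far, bRFS runs to that failure, and benign bounce describes a pattern without altering the event. Dependence of event status on later follow-up arises only if the analyst adds a cancellation rule that the documents do not contain.

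Were that rule added, each affected patient would shift the crude rate by 2.7 points, or the Kaplan-Meier estimate by 3.3 to 5.0 points with 30 to 20 at risk, not always upwards. Those sizes rest on invented PSA series, assumed risk sets and the minimum-rise reading of the 0.2. Nothing in the documents shows that any of the 37 patients is in the overlap. The conclusion rests on item 1 and the secondary endpoint meaning what they say when they name Phoenix without exception.

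### Acute toxicity is counted from 48 h to 3 months after an undefined procedure, so under either single starting point about one radiotherapy course falls outside both the acute and the late window

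*Combined protocol and SAP*

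**What the plan says.** All passages are in the combined protocol and SAP.

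- **STUDY VARIABLES DEFINITION, item 4**, the only definition of acute toxicity, covers the incidence and severity of GU and GI "adverse events from 48 h until 3 months after the procedure". The word procedure occurs nowhere else and is not defined.
- **Item 5** has a clear anchor: "Late toxicity defined as the maximal toxicity per patient more than 90 days after completion of RT".
- **Item 2** uses two explicit anchors. Biochemical relapse-free survival "was calculated from the time of first radiation treatment to failure, last follow-up or death", while the PSA nadir is taken after treatment completion.
- **Rules stated for late effects only.** Item 5 gives the visit and scoring rule: "Late adverse effects of radiation assessed at each follow-up visit using the radiation morbidity scoring criteria". The methods paragraph after item 5 gives the incidence formula: "The incidence of late adverse effects was calculated as the occurrence of the maximum grade toxicity per patient divided by the number of patients".
- **Primary objectives**, second bullet: "To maintain or decrease the incidence of acute and late urinary rectal complications despite increased dose (focal) radiotherapy". The Hypothesis likewise claims no significant increase in either acute or late toxicity.

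**The concern.** Acute and late windows should meet, so that every GU/GI event after the start of treatment belongs to one of them. Here the late window is tied to completion of RT and the acute window to an undefined event. Item 2 speaks of a first radiation treatment, so the course has more than one treatment, and its start and completion are different times. Where the acute window lies, and what falls between it and the late window, then depends on a choice the plan does not make.

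Acute toxicity is half of the second primary objective and part of the safety claim in the Hypothesis. An event that arises and resolves in a gap appears in neither rate. Two analysts could also obtain different acute rates from the same records, each following item 4 as written. Late toxicity keeps its own anchor and is not affected.

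**Working it through.** **Inputs**
- Acute window: 48 h (2 days) to 3 months after the procedure (item 4).
- Late window: more than 90 days after completion of RT (item 5).
- Three calendar months: m = 89 to 92 days, depending on the start date.
- Course length: L days from first to last treatment. The documents do not give it, so 7 to 56 days is assumed to show the range.

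Put day 0 at the first treatment and day L at completion. Late toxicity starts after day L+90. Uncounted time is the time from day 0 that lies in neither window.

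**(a) Procedure = completion of RT.** The acute window is day L+2 to day L+m.
- Before it: L+2 days, namely the whole course and the next 48 h.
- Between acute and late: max(0, 90−m), which is 1 day if m = 89 and otherwise 0.
- Total: L+2 to L+3 days.

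**(b) Procedure = first treatment.** The acute window is day 2 to day m.
- Before it: 2 days.
- Between acute and late: (L+90)−m days.
- Total: 2 + L + 90 − m. With m = 92 this is L; with m = 89 it is L+3.
- Treatment-period toxicity after the first 48 h does count as acute here, for a course of up to about 3 months. The main gap comes later, between 3 months after the start and 90 days after completion.

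**(c) 48 h from the start, 3 months from completion.** The acute window is day 2 to day L+m.
- Total: 2 + max(0, 90−m) = 2 to 3 days.

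| Assumed L (days) | (a) uncounted days | (b) uncounted days | (c) uncounted days |
|---|---|---|---|
| 7 | 9–10 | 7–10 | 2–3 |
| 28 | 30–31 | 28–31 | 2–3 |
| 40 | 42–43 | 40–43 | 2–3 |
| 56 | 58–59 | 56–59 | 2–3 |

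Under either single anchor the uncounted time is about one course, whatever L is. The one-day differences only reflect 3 months against 90 days and are unimportant.

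**With the window proposed below.** Acute runs from day 0 to day L+90, and late starts after day L+90. Uncounted time is 0 days and overlap is 0 days for every L.

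These are calendar days, not event rates. Item 4 does not say whether an event that began earlier and is still present when the window opens is counted. If it is, only events that both arise and resolve inside a gap are lost.

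**The case against.** The strongest reply is that this is one loosely used word. Under reading (c), which a clinician might well intend, nearly all treatment-period toxicity is acute and only 2 to 3 days are lost. The documents give no event times or rates, so no effect on the result can be shown. The length of the gap is also largely the assumed course length restated. All of this is fair, and it limits the claim to a conditional one. It does not remove the problem: item 4 states one anchor, not two, and nothing else in the documents selects (c).

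A reader might infer more than the text supports:

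- *That the procedure naturally means completed RT, so treatment-period toxicity is excluded.* The argument would be that item 2 names the first treatment when it means the start. But items 2 and 5 also name completion when they mean the end, so the same argument counts against completion. The treatment period as a whole is lost only under (a).
- *That the acute rate is materially understated, or biased between groups.* Any event lost to a gap lowers the rate, but neither the number lost nor its split between groups can be derived.

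Two further objections stand and shape the fix. Item 4 is in the past tense, so the window may already have been applied and should not be silently replaced. A corrected window also does not supply an acute grading scale, visit schedule or denominator, since the stated rules for these concern late effects.

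**Conclusion.** The point holds in conditional form. Item 4's anchor is undefined and the documents do not settle it. If it is completion of RT, L+2 to L+3 days lie in neither window. If it is the first treatment, L to L+3 days do. For an assumed course of 7 to 56 days these are 9 to 59 and 7 to 59 days. The unstated two-anchor reading leaves 2 to 3 days.

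Confidence is high that the term is undefined and that either single anchor leaves a gap of about one course; this does not depend on L. The direction is known only in that events lost to a gap lower the acute rate. The size of that effect is unknown. Because the rate serves a primary objective, and the stated rule can drop events from it, the wording should be corrected.

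**What to change.** In item 4, define acute toxicity as the incidence and worst grade of GU/GI events from the first radiation fraction through day 90 after completion of RT, and apply this to all groups compared. Remove the 48 h start and the undefined term. Leave item 5 unchanged; the two windows then meet exactly.

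Because item 4 is written in the past tense:

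- state which window was actually used;
- report the re-derived acute rate as a disclosed change, beside the rate from the window used;
- if grades during treatment were not recorded, state that the acute rate excludes on-treatment toxicity.

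**Cost:** one reworded item, and a re-derivation from treatment-period records if they exist. The documents give no on-treatment visit schedule, so they may not; the cost is then one stated limitation. The downside for the sponsor is that the acute rate may be higher.

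### Acute and late toxicity are defined without a pre-radiotherapy grade or an attribution rule, so persistent pre-existing urinary or bowel symptoms may be counted as toxicity

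*Combined protocol and SAP*

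**What the plan says.** All references are to the combined protocol and SAP.

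- **Primary objectives.** The safety aim is "To maintain or decrease the incidence of acute and late urinary rectal complications despite increased dose (focal) radiotherapy". No reference rate or margin is attached to it.
- **Study Variables Definition, item 4.** Acute toxicity covers GU and GI "adverse events from 48 h until 3 months after the procedure". No pre-treatment reference is named.
- **Item 5.** The late endpoint is "Late toxicity defined as the maximal toxicity per patient more than 90 days after completion of RT". On how it is graded, the item continues: "Late adverse effects of radiation assessed at each follow-up visit using the radiation morbidity scoring criteria" of EORTC/RTOG, together with CTCAE. Grading is tied to follow-up visits, and no pre-treatment grading is mentioned.
- **Paragraph after item 5.** Incidence is "the occurrence of the maximum grade toxicity per patient divided by the number of patients in each arm". For timing, "The cumulative incidence method was used to estimate time to late toxicity, and treatment groups were compared using the log-rank test", with death as a competing risk. The arms and treatment groups are not defined.
- **Item 3.** Imaging response, by contrast, is "evaluated by mpMRI at 12 months after radiotherapy and compared to the baseline scans".

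**The concern.** The safety objective asks what the focal boost does to complication rates. That calls for events that arise or worsen after treatment. The written rule records the worst grade after day 90 whatever the man's state at entry. Read literally, a man with unchanged grade 2 urinary frequency scores the same as a man who goes from grade 0 to grade 2.

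Three results could be affected:

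- the absolute incidence;
- the time-to-toxicity curve, because a symptom that predates RT would register at the first follow-up visit after day 90, a date set by the visit schedule and not by the onset of radiation injury;
- any between-group comparison, where background symptoms could mask a real difference or create a false one.

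Item 3 shows that the authors named a baseline comparison where they meant to use one.

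**Working it through.** **No plan figure to reproduce.** The only design figure is the sample size of 37. The documents give no toxicity rate, margin, alpha, power or baseline symptom prevalence. The check is therefore a reading of the definitions, followed by a hypothetical illustration of size.

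**Reading.** The late definition, the grading sentence, the incidence estimator, the cumulative-incidence sentence and the acute definition were each checked for a pre-RT grade, a change from baseline, or a rule restricting events to new or worsened ones. None contains any of these. The text at these points is unbroken and shows no sign of removed material.

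**Inputs for the illustration.**
- n = 37, from the stated sample size, treated as one group because the arms are undefined.
- r = true incidence of new toxicity at the counted grade. Assumed, range 5% to 20%.
- b = share of men whose pre-existing symptoms at that grade persist past day 90. Assumed, range 5% to 30%.
- b and r are assumed independent, and every persistent baseline symptom is assumed to be scored as an event.

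**Single group.** Counted rate = b + (1 − b)r. Excess = b(1 − r). With r = 10%, the true count is 0.10 × 37 = 3.7 men.

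| b | Counted rate | Men counted of 37 |
|---|---|---|
| 0% | 10% | 3.7 |
| 5% | 0.05 + 0.95 × 0.10 = 14.5% | 5.4 |
| 10% | 0.10 + 0.90 × 0.10 = 19% | 7.0 |
| 20% | 0.20 + 0.80 × 0.10 = 28% | 10.4 |
| 30% | 0.30 + 0.70 × 0.10 = 37% | 13.7 |

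Over the full assumed ranges the excess runs from 37 × 0.05 × 0.80 = 1.5 men to 37 × 0.30 × 0.95 = 10.5 men. For scale, the 95% half-width around 10% with 37 men is 1.96 × √(0.10 × 0.90 / 37) = 9.7 points. The 9-point excess at b = 10% is nearly as large.

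**Two groups, same b.** Counted difference = (1 − b)(r1 − r0). Take a true 20% against 10% (difference 10 points, risk ratio 2.0).
- b = 10%: 28% against 19%, difference 9 points, ratio 1.47.
- b = 20%: 36% against 28%, difference 8 points, ratio 1.29.
- b = 30%: 44% against 37%, difference 7 points, ratio 1.19.

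**Two groups, different b, same r = 10%.** Counted difference = (b1 − b0)(1 − r). With b of 20% against 10%, this is 0.10 × 0.90 = 9 points where there is no true difference. Reversing the groups gives −9 points.

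**The case against.** The strongest reply is that item 5 does not grade every symptom. It refers to "Late adverse effects of radiation assessed at each follow-up visit using the radiation morbidity scoring criteria", and on a plain reading a man with unchanged pre-RT nocturia has no effect of radiation to score. The word incidence and the time-to-event analysis also fit events that arise after treatment. This stands in part: investigators may well have left pre-existing symptoms out. But no attribution rule is given and no baseline grade is specified, so whether and how that was done cannot be checked or reproduced.

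A reader might infer something stronger: that pre-existing symptoms are counted, and that the safety result is therefore biased. The documents do not support this. They leave room for attribution, give no prevalence of symptoms at entry, and name no grade threshold.

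The direction is not fixed either. In a single group the error can only overstate toxicity, which works against a favourable safety claim. Between groups with the same baseline prevalence it pulls toward no difference, and modestly so at b = 10% (10 points become 9). A large false difference needs unequal prevalence, which is again an assumption.

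A further fair objection concerns the remedy. Subtracting a baseline grade from an overall GU or GI maximum would miss a man with grade 2 frequency at entry who later develops new grade 2 bleeding, since his maximum does not rise. This stands, and it means that the comparison has to be made symptom by symptom.

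The missing reference rate and the undefined arms are separate gaps, and closing them would not settle this one.

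**Conclusion.** The point holds as a weakness in the stated toxicity definitions, not as a demonstrated bias. Neither the late definition and its estimator nor the acute definition refers to a pre-RT grade, and the attribution that item 5 implies has no rule behind it. Persistent pre-existing symptoms may therefore enter the toxicity counts. If they do, absolute incidence is overstated, some event times mark the visit schedule instead of onset, and a between-group comparison may be diluted or confounded.

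The size cannot be obtained from the documents. The 19% in place of 10% (7.0 in place of 3.7 of 37 men) is hypothetical. It requires 10% of men to have persistent symptoms at the counted grade, independence from new toxicity, and all of those symptoms being scored. If no man has such symptoms, or if attribution removes them all, the bias is zero. Even so, a primary safety objective rests on these definitions, and a better rule is available at little cost.

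**What to change.** 1. Grade each GU and GI symptom before the first RT fraction, on the EORTC/RTOG and CTCAE scales that the plan already names. For men already treated, take the grade from the chart.
2. Count as an acute or late event any symptom that is new, or worse than that same symptom's baseline grade. Compare symptom by symptom, not on an overall GU or GI maximum.
3. Use these events for both the incidence and the time-to-toxicity analyses.
4. Report the unadjusted maximum grade alongside, so that nothing in the present analysis is lost.
5. Report the number of men without a baseline grade.

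The cost is a little more scoring work and one more column in the toxicity tables. The plan is at version 8 and written largely in the past tense, so much of the baseline grading may have to be retrospective and may be incomplete. That is the reason for step 5. Treatment is not affected.
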